#### 9.4.2 Analysis of Safety

##### 9.4.2.1 Analysis of adverse events

Safety analyses will be performed on the Safety Population. Adverse events will be coded using the Medical Dictionary for Regulatory Activities (MedDRA). Incidences (number and percent) of treatment-emergent adverse events (TEAEs), those events that start after dosing or worsened in severity after dosing, will be presented by treatment. Incidences of TEAEs will also be presented by maximum severity and relationship to study medication.

Similar presentations will be provided for SAEs, adverse events leading to withdrawal from the study, or adverse events leading to death. Analysis of adverse event data will include examination of the incidence rates of index shoulder-related TEAEs.

##### 9.4.2.2 Other safety analyses

Laboratory data and vital sign information will be summarized by treatment and will be presented as descriptive summary statistics for value and change from Baseline at each individual time point.

#### 9.4.3 Interim Analyses

For each shoulder condition, a blinded interim analysis will occur when approximately 50% of the patients have completed Week 8 to determine the need for a potential adjustment to the sample sizes. Prior data suggest the standard deviation of the primary endpoint could range from 2 to 2.5. Therefore, the interim analyses will enable a sample size increase up to 150 in each shoulder condition to ensure the desired statistical power is obtained.

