#### **SAMPLE SIZE DETERMINATION:**

Approximately 250 patients will be randomized in a 1:1 ratio to either FX006 or placebo (approximately 136 patients with glenohumeral OA and approximately 114 patients with shoulder AC). Sample sizes were estimated to yield a statistically significant difference ( $\alpha = 0.05$ , 2-sided) between the FX006 and placebo groups in the average daily shoulder pain with movement score at Week 12 (the first secondary endpoint for each shoulder condition). For glenohumeral OA, the true difference between the groups was assumed to be 1, with a standard deviation of 2, based on data observed in knee OA studies of FX006 and taking into consideration the clinical significance of a 1-point difference between the treatment groups. For shoulder AC, the true difference between the groups was assumed to be 1.2, with a standard deviation of 2.1, based on a review of the existing literature. The primary endpoint analyzing the AUC for the weekly mean of the average daily shoulder pain with movement score over 8 weeks should, therefore, have >80% power to show a significant difference between the FX006 and placebo groups. As the 2 shoulder conditions (glenohumeral OA and shoulder AC) are combined into 1 protocol strictly for ease of administration, all statistical testing will be performed separately for each shoulder condition and the overall type I error rate will be controlled at the  $\alpha = 0.05$  level within each shoulder condition.

For each shoulder condition, a blinded interim analysis will occur when approximately 50% of the patients have completed Week 8 to determine the need for a potential adjustment to the sample sizes. Prior data suggest the standard deviation of the primary endpoint could range from 2 to 2.5. Therefore, the interim analyses will enable a sample size increase up to 150 in each shoulder condition to ensure the desired statistical power is obtained.

---

**SITES:** Approximately 35 study sites in the United States

---

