### 4.3 Withdrawal Criteria

If a patient withdraws, he/she should continue to be followed for safety assessments up to 24 weeks after treatment. A patient may withdraw from the study at any time for any reason, without any consequences. In addition, a patient may be withdrawn from the study for the following reasons:

- Adverse event (typically a serious adverse event [SAE])
- Patient choice (withdrawal of consent, Investigator will attempt to ascertain reason)
- Protocol violation/noncompliance
- Lack of efficacy (lack of expected or desired effect related to a therapy)
- Physician decision (a position, opinion, or judgment reached after consideration by a physician with reference to the patient)
- Progressive disease (a disease process that is increasing in extent or severity)
- Study terminated by Sponsor
- Technical problem (a problem with some technical aspect of a clinical study, usually related to an injection)
- Other

If a patient withdraws from the study, he/she may request destruction of any samples taken and not tested, and the Investigator must document this in the study site records.

If a patient withdraws prematurely from the study due to the above criteria or any other reason, study staff should make every effort to complete the full panel of assessments scheduled for the EOS Visit (Week 24) (see Section 6.6). The reason for patient withdrawal must be documented in the electronic case report form (eCRF). Those patients who withdraw from the study will be referred to a physician for follow-up care.

Withdrawn patients will not be replaced.

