## 9.4 Statistical Methods

### 9.4.1 Analysis of Efficacy

#### 9.4.1.1 Primary efficacy analyses

For each shoulder condition, the primary AUC endpoint will be calculated and comparisons will be estimated from an Analysis of Covariance model with parameters for treatment group, Baseline average daily shoulder pain with movement score, and analysis site. In addition, the model for shoulder AC will also include a covariate for pain duration since onset. Full details of the AUC analyses will be detailed in the SAP.

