#### 9.4.6 Sample Size Determination

Approximately 250 patients will be randomized in a 1:1 ratio to either FX006 or placebo (approximately 136 patients with glenohumeral OA and approximately 114 patients with shoulder AC). Sample sizes were estimated to yield a statistically significant difference ( $\alpha = 0.05$ , 2-sided) between the FX006 and placebo groups in the average daily shoulder pain with movement score at Week 12 (the first secondary endpoint for each shoulder condition). For glenohumeral OA, the true difference between the groups was assumed to be 1, with a standard deviation of 2, based on data observed in knee OA studies of FX006 and taking into consideration the clinical significance of a 1-point difference between the treatment groups. For shoulder AC, the true difference between the groups was assumed to be 1.2, with a standard deviation of 2.1, based on a review of the existing literature. The primary endpoint analyzing the AUC for the weekly mean of the average daily shoulder pain with movement score over 8 weeks should, therefore, have >80% power to show a significant difference between the FX006 and placebo groups. As the 2 shoulder conditions (glenohumeral OA and shoulder AC) are combined into 1 protocol strictly for ease of administration, all statistical testing will be performed separately for each shoulder condition and the overall type I error rate will be controlled at the  $\alpha = 0.05$  level within each shoulder condition.

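### For glenohumeral OA, the re-estimation cap of 150 keeps 80% power only up to an SD of about 2.17, not over the plan's own range of 2 to 2.5

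*Combined protocol and SAP*

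**What the plan says.** Section 9.4.3 plans a blinded interim look in each condition when about half the patients have completed Week 8. It gives the reason as follows: "Prior data suggest the standard deviation of the primary endpoint could range from 2 to 2.5". From this it concludes that "the interim analyses will enable a sample size increase up to 150 in each shoulder condition to ensure the desired statistical power is obtained". The Synopsis (Sample Size Determination) makes the same statement.

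The power target and the effect sizes are in section 9.4.6. The study was sized on the Week 12 pain score, the first secondary endpoint: "For glenohumeral OA, the true difference between the groups was assumed to be 1, with a standard deviation of 2". The corresponding AC figures are a difference of 1.2 and an SD of 2.1. The primary AUC endpoint, it then says, "should, therefore, have >80% power to show a significant difference between the FX006 and placebo groups". Planned enrolment is 136 for OA and 114 for AC, randomized 1:1.

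Section 9.4.1.1 specifies the primary model, in which the treatment effect is "estimated from an Analysis of Covariance model with parameters for treatment group, Baseline average daily shoulder pain with movement score, and analysis site". Section 4.3 adds: "Withdrawn patients will not be replaced". The plan gives no difference on the AUC scale, no dropout rate and no expected variance reduction from covariates.

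**The concern.** Section 9.4.3 presents the cap as the answer to the SD range: the SD may be as high as 2.5, and for that reason the sample may grow to 150. A reader will take this to mean that 150 patients are enough anywhere in the range. For OA the permitted growth is small, from 136 to 150, while the variance at SD 2.5 is more than half as large again as at SD 2.0.

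The re-estimation is the plan's only stated safeguard against a larger SD, and each condition is tested on its own. If the claim fails for OA, the stated protection against a false-negative result fails with it, and a negative OA result could be given more weight than it deserves.

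**Working it through.** **Inputs.** Two-sided alpha 0.05, power target above 80%, OA difference 1 and SD 2, AC difference 1.2 and SD 2.1, planned totals of 136 and 114 (all section 9.4.6). SD range 2 to 2.5 and cap of 150, i.e. 75 per arm (section 9.4.3).

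**Assumptions.** The Week 12 difference also holds for the AUC. The AUC is time-averaged onto the 0 to 10 scale, which is the scale on which an SD of 2 to 2.5 makes sense. No covariate gain and no dropout; both are varied below.

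**Formula.** Two-sample t-test with *n* per arm, difference *d* and SD *s*. The noncentrality is d / (s × √(2/n)) on 2n − 2 degrees of freedom, and power is the probability that the noncentral t statistic exceeds the two-sided 5% critical value in absolute size.

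**Step 1: reproduce the plan's claim.**
- OA, n = 68, d = 1, s = 2: noncentrality 2.915, power 82.5%.
- AC, n = 57, d = 1.2, s = 2.1: noncentrality 3.051, power 85.6%.

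Both exceed 80%, so the method agrees with section 9.4.6.

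**Step 2: OA at the cap (n = 75, d = 1).**

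| SD | Noncentrality | Power |
|---|---|---|
| 2.0 | 3.062 | 86.0% |
| 2.1 | 2.916 | 82.6% |
| 2.2 | 2.784 | 79.0% |
| 2.25 | 2.722 | 77.2% |
| 2.5 | 2.449 | 68.2% |

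Solving for 80% gives an SD of 2.172, and (2.172 − 2.0) / 0.5 = 34% of the stated range. A total of 162 patients is needed for 80% at SD 2.25, and 200 at SD 2.5. The normal approximation gives nearly the same: 80% up to SD 2.19, 68.8% at SD 2.5, and 198 patients.

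**Step 3: a comparison that needs no AUC difference.** The cap adds 150/136 = 1.103, about 10%, to the sample. Moving from SD 2.0 to 2.5 multiplies the variance by (2.5/2.0)² = 1.5625, about 56% more. Whatever the true difference, 150 patients keep the power that 136 have at SD 2.0 only up to 2.0 × √(150/136) = 2.10. Keeping it at SD 2.5 takes about 136 × 1.5625 ≈ 212 patients. This shows how far power erodes from its planned level; it does not by itself show that power falls below 80%.

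**Step 4: vary what the plan leaves open (OA, n = 75, SD 2.5).**
- AUC difference 0.9 / 1.0 / 1.1 / 1.15: power 59% / 68% / 76% / 80%.
- If 2 to 2.5 is a raw SD, covariates explaining 10% / 20% / 25% of the variance: 73% / 78% / 80%. Reaching 80% takes about 24.5%.
- Analysed patients reduced by 5% / 10%: 66% / 64%.

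**Step 5: AC at the cap (n = 75, d = 1.2).** Power is 83% at SD 2.5 and stays at 80% up to SD 2.6. The problem is confined to OA.

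**The case against.** The strongest objection is that the deciding input is not in the plan. The difference of 1 belongs to Week 12, the SD range belongs to an 8-week AUC, and section 9.4.6 claims only that primary power exceeds 80%, not that the AUC difference equals 1. Section 1.3.3 reports that in the knee the effect grew through Week 7, so the 8-week average and the Week 12 value may differ in either direction. An AUC difference of about 1.15 would rescue the cap; it would imply 91% power at 136 patients and SD 2, which does not contradict a claim of more than 80%.

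The planned ANCOVA could also recover power. At SD 2.25 the shortfall is under three percentage points, and covariates explaining about 7% of the variance, or a difference of 1.04, would close it. The dropout range may also be too harsh: withdrawals after Week 8 cost the primary endpoint nothing, and earlier ones may remain in the Full Analysis Set.

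Much of this stands as a caution. The small shortfalls in the middle of the range are sensitive to assumptions, and 5% or 10% withdrawal is not the same as 5% or 10% of analysed patients lost. It does not rescue the sentence. The plan states neither a difference near 1.15 nor a covariate gain near 25%. The Week 12 assumptions are its only basis for primary power, and on that basis the claim fails clearly at the upper end of the SD range. Nor does it help that the increase is merely permitted, because even the largest permitted increase falls short.

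**Conclusion.** The concern holds. On the only OA difference the plan states, the cap does not secure more than 80% power over roughly the upper two thirds of the plan's SD range (about 2.17 to 2.5). At SD 2.5 the type II error is about 32%, where the plan promises less than 20%.

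This rests on three conditions: the 1-point Week 12 difference applies to the time-averaged AUC, covariates bring no gain beyond the quoted SD, and no patients are lost. The first two could be relaxed in the plan's favour, but only by figures it does not give. What is wrong is a stated power property. The validity of the test and of the estimate is untouched, and the AC claim stands before dropout.

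**What to change.** In section 9.4.3 and the Synopsis, replace the assurance with a conditional statement, for example: *Assuming that the differences of 1.0 (OA) and 1.2 (AC) also apply to the time-averaged AUC, and before any gain from covariate adjustment or loss from dropout, 150 patients keep at least 80% power for an SD up to about 2.17 in OA and 2.6 in AC; in OA, power at an SD of 2.5 is about 68%.*

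Also state the assumed difference on the same time-averaged AUC scale as the SD, and say whether 2 to 2.5 is a raw SD or the residual SD of the planned ANCOVA. If the sponsor holds a different AUC difference or expects a covariate gain, state it and recompute the limits from it.

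The cost is a few sentences and one additional stated assumption. No patient, procedure or analysis changes. The only drawback is that the published OA power looks less favourable.

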#### 9.4.4 Final Analyses

All final analyses will be completed following database lock for each shoulder condition. Final analyses specified in the protocol and SAP will be completed and reported in the Clinical Study Report (CSR). Post-hoc, exploratory analyses may be completed to further understand and elucidate study results. Any post-hoc, exploratory analyses completed will be clearly identified as such in the final CSR.

#### 9.4.5 Subgroups and Covariates

Preplanned subgroup analyses including aspiration status, OA grade based on the Samilson-Prieto classification system, gender, and Baseline average daily shoulder pain with movement score will be detailed in the SAP. In addition, subgroups of pain duration since onset are preplanned for shoulder AC patients. Further subgroups may be defined and explored after all preplanned analyses have been completed to further elucidate study results.

Covariates for efficacy analyses will include Baseline average daily shoulder pain with movement score, Baseline score for the endpoint, analysis site, and, for AC patients, pain duration since onset. Other covariates may be explored and will be fully defined in the SAP.

#### 9.4.6 Sample Size Determination

Approximately 250 patients will be randomized in a 1:1 ratio to either FX006 or placebo (approximately 136 patients with glenohumeral OA and approximately 114 patients with shoulder AC). Sample sizes were estimated to yield a statistically significant difference ( $\alpha = 0.05$ , 2-sided) between the FX006 and placebo groups in the average daily shoulder pain with movement score at Week 12 (the first secondary endpoint for each shoulder condition). For glenohumeral OA, the true difference between the groups was assumed to be 1, with a standard deviation of 2, based on data observed in knee OA studies of FX006 and taking into consideration the clinical significance of a 1-point difference between the treatment groups. For shoulder AC, the true difference between the groups was assumed to be 1.2, with a standard deviation of 2.1, based on a review of the existing literature. The primary endpoint analyzing the AUC for the weekly mean of the average daily shoulder pain with movement score over 8 weeks should, therefore, have >80% power to show a significant difference between the FX006 and placebo groups. As the 2 shoulder conditions (glenohumeral OA and shoulder AC) are combined into 1 protocol strictly for ease of administration, all statistical testing will be performed separately for each shoulder condition and the overall type I error rate will be controlled at the  $\alpha = 0.05$  level within each shoulder condition.

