#### **1.3.3 Efficacy in Patients with Osteoarthritis of the Knee**

Efficacy data from 3 studies provide substantial evidence supporting the effectiveness of 32 mg FX006 in the management of OA pain. Results of the primary endpoint from the Phase 3, multicenter, adequate, and well-controlled study showed that patients treated with 32 mg FX006 had a rapid, durable, and meaningful analgesic response that was significantly better than

placebo-treated patients ( $p < 0.0001$ ). This finding was supported by a second smaller Phase 2b study where a highly similar pattern of response to 32 mg FX006 was demonstrated.

Robustness of the primary outcome in the Phase 3 study was further supported by the internal consistency demonstrated in favor of 32 mg FX006 through secondary analyses utilizing the primary outcome data (average daily pain) to evaluate durability and magnitude of response. These included least square mean (LSM) testing at each week and area under the effect curve analyses for Weeks 1 through 12 and Weeks 1 through 24. Results demonstrated that the analgesic effect of 32 mg FX006 was significant at Week 1, increased through Week 7, and was sustained through at least Week 16. Responder analyses further suggested that FX006 provided clinically relevant improvement from Weeks 1 through 16 relative to placebo.

Analyses utilizing data collected from other instruments or measures (i.e., Western Ontario and McMaster Universities Osteoarthritis Index [WOMAC], Patient Global Impression of Change [PGIC], Clinical Global Impression of Change [CGIC], and Knee Injury and Osteoarthritis Outcome Score [KOOS] Quality of Life [QOL]) provided additional insight into the effects on pain relief, as well as physical function and global well-being. At 32 mg, FX006 provided clinically relevant improvement relative to placebo through Week 12 for WOMAC and KOOS QOL and through at least Week 16 for PGIC and CGIC. Additionally, a significant reduction in rescue medication utilization in patients treated with 32 mg FX006 was of potential important clinical consequence and added a meaningful element to the overall effectiveness profile of 32 mg FX006. Collectively, these results provide substantial evidence to support 32 mg FX006 as an effective therapy for the management of OA knee pain.

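### The >80% power stated for the primary 8-week AUC is inferred from Week 12 inputs, and for OA it is not supported over most of the plan's own SD range

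*Combined protocol and SAP*

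**What the plan says.** Section 9.4.6 plans "approximately 136 patients with glenohumeral OA and approximately 114 patients with shoulder AC", randomized 1:1. The sizes were chosen to detect a difference "in the average daily shoulder pain with movement score at Week 12 (the first secondary endpoint for each shoulder condition"). The assumed difference is 1 with SD 2 for OA, from FX006 knee OA studies and a view of what is clinically significant. For AC it is 1.2 with SD 2.1, from the literature. The section then says that the primary AUC "score over 8 weeks should, therefore, have >80% power to show a significant difference between the FX006 and placebo groups". The synopsis repeats this.

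Three other places bear on the claim:

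- Section 9.4.3: "Prior data suggest the standard deviation of the primary endpoint could range from 2 to 2.5". A blinded interim look may raise each cohort to at most 150.
- Section 1.3.3, on the knee trial: the effect "was significant at Week 1, increased through Week 7, and was sustained through at least Week 16". No weekly effect sizes are given.
- Section 9.4.1.1: the primary test is an ANCOVA with Baseline pain and analysis site (plus pain duration for AC). Details of the AUC are left to the SAP.

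**The concern.** The word *therefore* carries a power figure from one endpoint to another. That works only if the effect averaged over 8 weeks, relative to the SD of the AUC, is at least as large as the Week 12 effect relative to the Week 12 SD. The plan never shows this. The one figure it gives for the primary endpoint, an SD of 2 to 2.5, starts at the OA Week 12 value and goes up from there.

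The primary test decides each cohort. If the OA comparison missed, readers would judge the result against a stated power above 80%. On the plan's own SD range that power could be in the 60s, and a null result would then be weaker evidence of no effect than it appeared.

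**Working it through.** **Inputs.** Two-sided alpha 0.05 and 1:1 allocation; OA 136 (68 per arm), difference 1, SD 2; AC 114 (57 per arm), difference 1.2, SD 2.1 (all 9.4.6). Primary-endpoint SD 2 to 2.5 and cap 150, or 75 per arm (9.4.3).

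**Scale.** The plan does not say whether the AUC is divided by time. An SD of 2 to 2.5 for an undivided 8-week AUC would mean only 2/8 = 0.25 to 2.5/8 = 0.31 points per week on average, which is hard to square with a Week 12 SD of 2. I therefore take the AUC as time-averaged, in NRS points. This is an assumption.

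**Formula.** For an unadjusted two-sample t-test, the noncentrality is difference / (SD × √(2/n per arm)) with 2n − 2 degrees of freedom. Power is the probability that the noncentral t exceeds the two-sided 5% critical value in absolute size.

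**1. The plan's figure, with Week 12 inputs.**
- OA: 1 / (2 × √(2/68)) = 2.915, power 82.5%.
- AC: 1.2 / (2.1 × √(2/57)) = 3.051, power 85.6%.

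The normal approximation gives 83.0% and 86.2%. The claim of >80% reproduces if these inputs carry over unchanged.

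**2. The SD range of 9.4.3, keeping the full assumed effect.**

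| Cohort, per arm | SD 2 | SD 2.1 | SD 2.25 | SD 2.5 |
|---|---|---|---|---|
| OA, 68 (planned) | 82.5% | 78.7% | 73.0% | 63.9% |
| OA, 75 (cap) | 86.0% | 82.6% | 77.2% | 68.2% |
| AC, 57 (planned) | 88.8% | 85.6% | 80.6% | 71.9% |
| AC, 75 (cap) | 95.5% | 93.5% | 90.1% | 83.2% |

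**3. Where 80% is lost.** At 68 per arm, 80% power needs a noncentrality of about 2.822.
- Largest OA SD at difference 1: 1 / (2.822 × √(2/68)) = 2.07. At the cap it is about 2.17.
- Smallest OA average difference at SD 2: 2.822 × 2 × √(2/68) = 0.97.
- Largest AC SD at difference 1.2 and 57 per arm: about 2.27.

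For OA, the part of the range above 2.07 is (2.5 − 2.07) / (2.5 − 2) = 86% of it.

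**4. The time course at SD 2 (illustration only).** Suppose the effect rises in a straight line from a fraction f of 1 point at Week 1 to 1 point at Week 7 and stays there. The mean over Weeks 1 to 8 and the OA power are then:
- f = 0.9: 0.96, 79%
- f = 0.8: 0.91, 75%
- f = 0.5: 0.78, 62%

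The values of f are mine. The documents give none.

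**The case against.** The strongest reply is that nothing is miscalculated: at an average difference of 1 and SD 2, power is above 80% in both cohorts. That stands. It limits several stronger readings.

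- **That the OA claim fails even at SD 2, or that the plan contradicts itself.** A reader might infer this from the rise through Week 7. But section 1.3.3 gives no weekly sizes, and a sustained effect need not mean that Week 12 equals Week 7. If Week 12 is 1.0, f is 0.8 and the Week 7 to 8 peak is 1.10, the 8-week average is 1.00 and power is 83%.
- **That the unadjusted test gives the whole answer.** The planned ANCOVA could help. If covariates explained 20% of the variance (assumed), OA power at f = 0.8 and SD 2 would be 84%. At 68 per arm with the full effect it would be 82% at SD 2.25 but still only 74% at SD 2.5. Averaging could also lower the SD: a weekly SD of 2 with within-patient correlation 0.8 (assumed) gives 2 × √((1 + 7 × 0.8)/8) = 1.82, and 83% at f = 0.8. The plan claims neither gain, and its SD of 2 to 2.5 for the primary endpoint shows no sign of the second.
- **That the knee build-up also lowers AC power.** The AC assumption comes from other literature, and no AC time course is given.
- **That losing a few OA patients breaks the claim.** The plan says "Withdrawn patients will not be replaced" and gives no dropout rate. But the FAS needs only one post-dose assessment, pain is recorded daily, and a withdrawal after Week 8 need not remove the 8-week AUC.

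The interim look is a partial answer. It responds to a larger SD, but for OA its cap restores 80% only up to an SD of about 2.17. Being blinded, it is not designed to detect a smaller average effect.

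**Conclusion.** The concern holds in this form: the primary's power is inferred from Week 12 without an AUC effect size, and for OA it is not supported over most of the SD range the plan itself gives. OA power with the full 1-point average difference runs from 82.5% (SD 2) to 64% (SD 2.5) at 136 patients, and is 68% at SD 2.5 at the cap. This rests on a time-averaged AUC, complete data and no credit for covariates.

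At SD 2 the claim is conditional: it holds if the 8-week average difference is at least 0.97. The knee time course points to a lower value but does not establish one.

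AC meets the claim up to an SD of about 2.27 at the planned size, and reaches 83% at SD 2.5 if raised to 150.

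The sponsor should correct the statement. It does not invalidate the design or the analysis.

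**What to change.** In section 9.4.6 and the synopsis:

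1. Delete *therefore*, and label 82% (OA) and 86% (AC) as power for Week 12 with complete data.
2. State the primary's power separately. Define the AUC scale (time-averaged, so that it shares units with the 1-point difference and the SD of 2 to 2.5), and give the 8-week average difference and missing-data rate that the sponsor chooses.
3. Show that power across SD 2 to 2.5. For OA with an average difference of 1 and complete data, it is about 64% to 82% at 136, and 68% at SD 2.5 with 150.
4. State any credit taken for covariate adjustment, and whether the SD of 2 to 2.5 is before or after adjustment.

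The cost is a wording change. No sample size change is needed. The downside is that the stated power for the OA primary becomes less favourable.
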